3.7.5.2. Profile of Mood States

The profile of mood states (POMS) was administrated at pre- and post-time points and assessed by requiring participants to rate their feelings on a 5-point Likert scale over the course

of 65 adjectives. The values of certain adjectives in the POMS are summed together to create values for 6 different domains: tension, depression, anger, fatigue, confusion, and vigor. A total mood disturbance score was also calculated by adding the values of all negative domains (tension, depression, anger, fatigue, confusion) and subtracting the vigor score (215). A constant of 100 was added to the total mood disturbance score to prevent a negative value.

3.7.5.3 Sleep Evaluation

Following day 1 of pre-testing, and approximately 3 days before post-testing measurements, participants were given an actigraphy watch (Fatigue Science Readiband™, Blaine, WA) to wear on their non-dominant wrist for 72 hours continuously. These data were used to assess sleep quantity and quality in their own environment (not in the laboratory). The outcome variables of this measure included total time sleeping, sleep latency (time in required to fall asleep in a resting state), and sleep efficiency (a measure of sleep quality, or the ratio of time spent asleep to the time spent in bed, including resting). The sleep efficiency measure is based on sleep latency and average number of wake episodes, with higher scores indicating better sleep quality (295). The actigraphy watch was chosen to measure sleep in favor of the more common method of administering the Pittsburgh Sleep Quality Index (PSQI), as previous studies have found that the PSQI does not correlate well with polysomnography (gold standard measure of sleep), while actigraphy watches have been validated against polysomnography (187, 223).

3.7.6 Nitrogen Balance

Nitrogen balance was analyzed at pre- and post-intervention testing points. After the day 1 visit, and after the taper session of week 12, participants were provided with a 3,000 mL 24-hour urine collection jug (VWR international, Radnor PA). Participants were instructed to store the urine collection jug in the refrigerator when not in use. After submission of the urine jug,

total volume (mL) was recorded and mixed via hand-inversion and aliquoted into two, 15-mL Falcon® tubes (Corning Inc., Corning, New York). Thereafter, samples were frozen in an -80° C freezer for later analysis using commercially available colorimetric detection assays (Thermo Fisher Scientific Inc., Carlsbad, CA). All assays were performed in duplicate. Intra-assays coefficients of variation (CV) were 1.24%, 2.19% and 1.60%. Nitrogen balance (NBAL) was calculated using the equation: $NBAL = [(protein\ intake\ (g)/6.25) - ((Urine\ urea\ nitrogen\ (g) + 5\ mg/kg\ body\ mass\ (fecal\ loss\ of\ nitrogen) + 2\ (miscellaneous\ loss\ of\ nitrogen)))]$ (165).

3.7.7 Insulin-like Growth Factor 1

To assess changes in free IGF-1, a venous blood sample (9 mL total) was collected from an antecubital vein into vacutainer tubes (Greiner Bio One International, NC) for plasma (EDTA) in the morning following an overnight fast on pre- and post-testing time points. Plasma was subsequently centrifuged at 1,000 g for 15 minutes at 4°C and stored in -80°C freezer for later analysis using commercially available ELISA kits (R&D Systems Inc., Minneapolis, MN). All assays were performed in duplicate. Intra-assays coefficients of variation (CV) were 6.71% and 5.52%, and the inter-assay CV was 13.07%. Intra-assay CVs were required to be less than 15% to be included in analysis.

3.8 Sample Size Justification and Statistical Analysis

An a priori analysis was conducted with an effect size F of 0.25 calculated using mean and standard deviations from previously reported changes in LBM in older men (350) with power set to 0.8 and α set to 0.05 for 3 groups and 3 measurements. With an expected dropout rate of 15% (110), a sample size of 36 was adequate and provided an even distribution between groups.

A one-way analysis of variance (ANOVA) was used to analyze baseline differences and total training volume among groups. A 3x2 mixed model ANOVA with group as the between subjects' factor (Post-ex, Pre-sleep, Ex only) and time as the within-subjects factor (pre and post) was performed on all dependent variables except for muscle thickness, 1-RM strength, muscle power, and appetite, where a 3x3 mixed model ANOVA (Post-ex, Pre-sleep, Ex only x pre, mid, post) was used. Pearson product-moment correlation, or Spearman's correlation in the event of normality violation, was used to determine the relationship between changes in free IGF-1 and changes in body composition, muscle thickness, 1-RM strength, muscular power, and cognitive assessments.

Outliers were removed and defined as values outside of the mean \pm 3 standard deviations. Data were tested for normality (Shapiro-Wilk), homogeneity of variances (Levene's test), and sphericity (Mauchly's test) where appropriate. When normality or homogeneity of variances was violated, non-parametric testing or data transformation was performed. For a mixed model ANOVA, if transformation could not correct the violation, original data were analyzed, as there are no non-parametric alternatives. When sphericity was violated, the main time and group x time interactions were interpreted with the Greenhouse-Geisser estimation.

Significance was set at $p \leq 0.05$. Trends were noted for p -values between 0.051-0.10. For significant interactions and main effects, pairwise comparisons with Bonferroni adjustments were conducted (296, 332). Pearson correlation coefficients (r) or Spearman's correlation coefficients (r_s) were interpreted as "negligible" = < 0.30 , "low" = $0.30-0.50$, "moderate" = $0.50-0.70$, "high" = $0.70-0.90$, and "very high" = > 0.90 (244). Percentage change was calculated as $((\text{post value} - \text{pre value}) * 100)$. All analyses were performed with SPSS version 25

(IBM Corp., Armonk, NY) and GraphPad Prism version 8.1.1 (GraphPad software, San Diego, CA). Data are presented as mean values \pm standard deviation, unless otherwise stated.

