3.3 Participants

Healthy, sedentary (not exercising regularly for the past 6 months), older adult males (N=30; Post-ex n=9, Pre-sleep n=11, Ex only n=10) between the ages of 60-75 years old from the Tallahassee area participated in the study. Health-related exclusion criteria included diagnosis of cardiac or peripheral vascular disease, stroke, kidney dysfunction, metabolic diseases, uncontrolled hypertension, orthopedic limitations, skeletal muscle complications, milk allergy, psychiatric conditions, use of psychotropic drugs or cognitive impairment. Additional exclusion criteria included participation in a structured regular exercise program within the past 6 months, actively attempting to increase or decrease body mass, scoring 26 points or less on the Montreal Cognitive Assessment, and/or body mass index (BMI) of ≥ 35 kg/m². To determine exclusion criteria, all participants completed an informed consent (appendix C), health history questionnaire (appendix E), physical activity questionnaire (appendix F), Montreal Cognitive Assessment (appendix G), and height and weight measurements, prior to any participation in the intervention. Lastly, all participants submitted a physician consent (appendix D) form prior to beginning the exercise training protocol.

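### The stated 80% power with 36 men does not carry over to the planned lean-mass analysis, which uses two visits rather than three, and it falls to about 20–23% if the effect size is on the change scale

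*Combined protocol and SAP*

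**What the plan says.** Section 3.8 gives the only power statement in the plan. It uses an "effect size F of 0.25 calculated using mean and standard deviations from previously reported changes in LBM in older men", "with power set to 0.8 and α set to 0.05 for 3 groups and 3 measurements". It then concludes: "With an expected dropout rate of 15% (110), a sample size of 36 was adequate". It does not name the test that was powered (group-by-time interaction, time effect or group effect), the within-person correlation, the sphericity value or the number of completers required. It also does not say whether the SDs behind f were SDs of change or of lean mass at a visit.

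The same section assigns the analyses. A 3x2 (pre, post) mixed ANOVA "was performed on all dependent variables except for muscle thickness, 1-RM strength, muscle power, and appetite"; those four get a 3x3 model. Lean mass is not among the four. Section 3.7.1 agrees, since it places the body-composition measurements at the pre- and post-intervention points only. Section 3.3 reports the men who took part: "N=30; Post-ex n=9, Pre-sleep n=11, Ex only n=10".

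**The concern.** Two features of the sizing do not match the analysis of the variable it is based on.

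- **Scale.** An effect size built from means and SDs of change has already used the correlation between a man's two measurements. A repeated-measures formula expects f in raw-score SD units and brings the correlation in itself, through a factor m/(1−ρ), where m is the number of visits. A change-scale f entered there is credited with the correlation twice.
- **Number of visits.** The calculation uses three measurements, but lean mass has two.

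The aim in Section 3.1 is a comparison between arms. If the power of that comparison is well below 80%, a null result for protein timing could be read as a well-powered negative when only large differences could have been detected.

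**Working it through.** **Inputs from the documents.** f=0.25, α=0.05, target power 0.80, k=3 groups, m=3 measurements, 15% dropout, N=36 (Section 3.8); 30 men took part (Section 3.3); lean mass at two visits (Sections 3.7.1 and 3.8). **Assumed.** Within-person correlation ρ, for which the plan gives no value, and sphericity (ε=1).

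**Formulas (noncentral F).**
- Repeated measures, raw-score f: λ = f²·N·m/(1−ρ). Interaction df are (k−1)(m−1) and (N−k)(m−1). Time-effect df are m−1 and (N−k)(m−1).
- One-way ANOVA on change, change-scale f: λ = f²·N, df 2 and N−3.

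**Step 1. Reproduce 36.** Three raw-score, three-visit routes were found.

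| Route (m=3) | Needed for 80% | With 15% dropout |
|---|---|---|
| Interaction, ρ=0.5 | 35, balanced 36 (82.3%) | 43, so 36 has no allowance |
| Interaction, ρ=0.6 | 28, balanced 30 | 30/0.85 = 35.3, so 36 |
| Time effect, ρ=0.5 | 28, balanced 30 | 30/0.85 = 35.3, so 36 |

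For the first row, λ = 0.0625 × 36 × 3/0.5 = 13.5 on 4 and 66 df. The other forms tried do not come near 36: one-way on change needs 158 (159 balanced), partial-eta-squared forms need 99 to 195, and the between-group test needs 57 or more. So 36 came from a raw-score f in a repeated-measures formula, or from something the text does not describe.

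**Step 2. If the SDs were of changes.** With two visits the interaction test is the one-way ANOVA on change.
- N=36: λ = 0.0625 × 36 = 2.25, df 2 and 33, power 23.1%.
- N=31 (36 × 0.85 = 30.6): power 20.1%.
- N=30: λ = 1.875, df 2 and 27, power 19.5%.

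**Step 3. If the SDs were raw.** Keep f=0.25 and each route's own ρ, but set m=2 to match the lean-mass analysis.

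| Route | N=36 | N=30 |
|---|---|---|
| Interaction, ρ=0.5 | 72.9% | 63.5% |
| Interaction, ρ=0.6 | 82.6% | 73.9% |
| Time effect, ρ=0.5 | 82.9% | 75.2% |

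For the first cell, λ = 0.0625 × 36 × 2/0.5 = 9 on 2 and 33 df. In the second and third routes the 36 already includes dropout, so the N=30 column is the relevant one. In the first route 36 is the number of completers required, so 72.9% applies only if nobody is lost.

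**Step 4. What the design can detect.** Solving the one-way formula for 80% power gives a change-scale f of 0.60 at N=30 and 0.54 at N=36. If one arm differs from two equal arms, the difference is f × 3/√2. If the three arms are evenly spaced, the extremes differ by f × √6.
- N=30: 0.60 × 2.121 = 1.27 to 0.60 × 2.449 = 1.47 SD of change.
- N=36: 0.54 gives 1.15 to 1.33 SD of change.

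These figures treat the arms as equal in size; the actual split is 9/11/10.

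**The case against.** The strongest objection is that the text does not fix the scale. Means and SDs from reported changes could be pre and post means with raw SDs, taken from a study that reported changes. Nothing is then counted twice, and power is that of Step 3. Only the cited study could settle this. This objection stands: a reader might infer that power is simply near 20%, but the documents support that only as the consequence of one reading, albeit the more natural one.

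A reader might also reject the raw-score reading because of the size of effect it implies. With raw f=0.25 and two visits, the arms would have to differ in lean-mass change by 1.06 to 1.22 raw SD, or 5.3 to 9.8 kg for an assumed raw SD of 5 to 8 kg. The plan gives no lean-mass SD and no benchmark for a plausible gain, and the figure presumes that the interaction was the test powered. It is suggestive at most.

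Nor do the documents show that dropout was left out. That follows only for the interaction at ρ=0.5. At ρ of about 0.6, or for the time effect at ρ=0.5, a 15% allowance fits within 36.

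Finally, a higher ρ raises raw-score power: the two-visit interaction reaches 85.8% at N=30 with ρ=0.7. That is correct, but at ρ=0.7 the three-visit interaction needs only 24 balanced, or 29 with dropout, so it does not explain the stated 36.

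**Conclusion.** The concern holds in conditional form. The claim that 36 men give 80% power does not describe the planned lean-mass analysis.

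- With SDs of change, power is about 23% at N=36 and 20% at N=30, because the correlation is counted twice.
- With raw SDs, each route found to 36 falls below 80% with two visits at the number of completers it allows for: 72.9% (63.5% at N=30), 73.9% and 75.2%. The last concerns the time effect averaged over the arms, not protein timing.

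The mismatch between three and two visits rests on the documents alone. The percentages under raw SDs rest on assumed values of ρ and on sphericity in the three-visit sizing, and the choice between the two branches rests on a source not available here. The shortfall is therefore modest on one reading and severe on the other, and the plan does not give enough to tell which.

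**What to change.** Rewrite the sample-size paragraph of Section 3.8 so that it:

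1. recomputes power for the 3x2 group-by-time test on lean mass, that is, a one-way comparison of change;
2. states whether the SDs taken from the cited study are of change or of raw lean mass, the correlation assumed if any, and the number of completers required;
3. uses the number of men actually analysed. Section 3.3 gives 30 who took part, but the 80% compliance rule (Section 3.5) and the removal of outliers (Section 3.8) may lower it;
4. replaces the statement of adequacy with the detectable difference: at 80% power, a change-scale f of about 0.60 at N=30 (1.27 to 1.47 SD of change between arms) or 0.54 at N=36 (1.15 to 1.33 SD).

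The cost is one reworded paragraph and a less favourable stated figure. No extra enrolment or change of procedure is needed.

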3.1 Overview of Experimental Design

The overarching aim of this project was to compare the traditional recommendation of immediate post-exercise protein consumption with nighttime pre-sleep protein intake during 12 weeks of resistance training on functional and cognitive adaptations in older adults. To achieve this, our design contained three groups who performed the same 12-week RET program two times per week and: 1) Consumed protein immediately post-exercise (Post-ex), 2) Consumed protein 30 minutes prior to sleep (Pre-sleep), or 3) Did not consume additional protein – exercise only (Ex only). Baseline total kilocalories (kcal) and protein intake were monitored to ensure no significant differences among groups occurred. The dependent variables consisted of pre- to post-intervention changes in body composition (i.e. lean mass, fat mass, and percent body fat), functional capacity (i.e. SPPB), nitrogen balance, free plasma insulin-like growth factor 1 (IGF-1), profile of mood states, and sleep evaluation, and digit symbol substitution and pattern comparison. Pre-, mid-, and post-intervention 1-RM, muscular power, and muscle thickness were assessed to determine the time course of muscular adaptations and appetite changes.

The pre-intervention measures took place over 2-3 days. All participants were instructed to refrain from vigorous physical activity at least 48 hours prior to all pre-testing measurements. On day 1, participants reported to the laboratory in the morning following an overnight fast (participants were encouraged to consume normal water intake) to complete the informed consent process, health history, and physical activity questionnaires. Thereafter, participants completed pre-training assessments including height and weight, baseline blood pressure, psychological and cognitive assessments, blood draw (IGF-1), body composition (DXA or BIA),

muscle thickness, muscular power, and the SPPB. Following the completion of day 1 assessments, participants were provided a 3-day food record, actigraphy watch, and 24-hour urine collection jug (nitrogen balance) to return prior to beginning the RET portion of the study.

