Day 2 took place approximately 72-96 hours after the first visit and served as a familiarization session for maximum strength testing. Day 3 took place 5-7 days after day 2 and included retesting maximum strength. Some participants elected to complete the first maximum strength test at the end of day 1, in which case, they were instructed to return 5-7 days later to retesting maximum strength, resulting in only 2 pre-testing visits. Thereafter, participants completed 12 weeks of RET, with or without protein supplementation, in the Strength Training Laboratory of the Sandels building. Participants completed post-intervention measures during week 12 in a similar manner as pre-intervention. Maximum strength, muscle power, and muscle thickness were also assessed after week 6 of RET.

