3.2 Methods for Specific Aims

3.2.1 Specific Aim 1: Body Composition and Functional Capacity

Specific aim 1 was to examine the degree to which timing of protein intake influenced body composition, muscle thickness, and functional capacity during 12 weeks of RET in older adults.

Dependent Variables (Detailed protocols for each assessment are provided in the subsequent sections)

- Body composition
 - Lean mass
 - Fat mass
 - Percent body fat

- Muscle thickness
- Functional capacity
 - SPPB
 - Balance
 - Gait speed
 - 5-chair stand
 - Maximum muscular strength
 - Muscular power

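### The power calculation pairs a lean-mass effect size with three measurements, but lean mass is measured twice and tested in a 3×2 ANOVA, so the stated 0.80 does not describe that test

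*Combined protocol and SAP*

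**What the plan says.** Section 3.8 describes the a priori calculation as using "an effect size F of 0.25 calculated using mean and standard deviations from previously reported changes in LBM in older men", with power 0.8 and alpha "0.05 for 3 groups and 3 measurements". It concludes: "With an expected dropout rate of 15% (110), a sample size of 36 was adequate and provided an even distribution between groups". It gives no correlation among repeated measurements, no sphericity correction for the power calculation, and no statement of which F test (time, or group by time) was powered.

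On lean mass, the other passages agree with one another:

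- Section 3.1 says that the "dependent variables consisted of pre- to post-intervention changes in body composition (i.e. lean mass, fat mass, and percent body fat" and further items. Lean mass is thus a two-point outcome.
- Section 3.1 limits the mid-study assessment: "Maximum strength, muscle power, and muscle thickness were also assessed after week 6 of RET".
- Section 3.7.1 places body composition at the pre- and post-intervention visits only.
- Section 3.8 says the 3×2 (pre, post) ANOVA "was performed on all dependent variables except for muscle thickness, 1-RM strength, muscle power, and appetite". Lean mass is not among the exceptions, so it falls under the 3×2 model.

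Specific Aim 1 (section 3.2.1) asks how far "timing of protein intake influenced body composition, muscle thickness, and functional capacity during 12 weeks of RET in older adults". Body composition is the first item in its list.

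**The concern.** The number of measurements enters both the noncentrality parameter and the degrees of freedom of a repeated-measures F test. A power figure for three measurements is therefore not a power figure for two. There are two readings of section 3.8. If the calculation was meant for lean mass, it has one measurement too many. If it was meant for the outcomes with a mid-study measurement, a lean-mass effect size was applied to other outcomes without saying so. On either reading, the effect size and the powered design do not belong to the same planned test.

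This is the only power basis in the plan. A reader who interprets a lean-mass group-by-time result, especially a null one, could rely on a 0.80 that was not computed for it.

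**Working it through.** **Inputs from section 3.8:** f = 0.25, alpha = 0.05, power 0.80, k = 3 groups, m = 3 measurements, 15% dropout, total 36. **From section 3.3:** 30 participants (9, 11 and 10 per group). **Assumed, because not stated:** the correlation ρ between measurements (taken over a range), f on the usual repeated-measures scale, equal groups, sphericity, and the group-by-time test as the target.

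**Formula.** λ = f²·N·m/(1−ρ), df1 = (k−1)(m−1), df2 = (N−k)(m−1). Power is the probability that a noncentral F with these values exceeds the 5% critical value.

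**Step 1: reproduce 36 with three measurements.**

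- At ρ = 0.5, 35 completers are needed, or 36 when rounded to equal groups. At N = 36, λ = 0.0625×36×3/0.5 = 13.5 on 4 and 66 df, and power is 0.82. Here 36 is the number *before* dropout; 35/0.85 = 41.2, so 42 would be enrolled.
- At ρ = 0.6, 28 completers are needed, or 30 in equal groups. Then 30/0.85 = 35.3, which rounds up to 36 *including* dropout. The time main effect at ρ = 0.5 leads to the same 28, 30 and 36.

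So 36 is reachable, but only with inputs that the plan leaves out. It is not an arithmetic error.

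**Step 2: same inputs, two measurements.**

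- N = 36, ρ = 0.5: λ = 0.0625×36×2/0.5 = 9.0 on 2 and 33 df; power 0.73 (three measurements: 0.82).
- N = 30, ρ = 0.6: λ = 0.0625×30×2/0.4 = 9.375 on 2 and 27 df; power 0.74 (three measurements: 0.83).

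**Step 3: the range.** Group-by-time power, three versus two measurements:

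| ρ | N = 30 | N = 36 | Completers for 0.80 |
|---|---|---|---|
| 0.5 | 0.73 / 0.64 | 0.82 / 0.73 | 35 / 42 |
| 0.6 | 0.83 / 0.74 | 0.91 / 0.83 | 28 / 35 |
| 0.7 | 0.93 / 0.86 | 0.97 / 0.92 | 22 / 27 |
| 0.8 | 0.99 / 0.96 | 1.00 / 0.99 | 16 / 19 |

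The 3×2 test reaches 0.80 at ρ of about 0.65 for N = 30 and 0.57 for N = 36. At ρ = 0.85 and N = 30 the loss is under one point (0.999 versus 0.992). Simulation of the 3×2 test with 10 per group gave 0.64, 0.74, 0.86 and 0.97 at ρ = 0.5, 0.6, 0.7 and 0.8. With 9, 11 and 10 per group and one assumed linear pattern of means it gave 0.61, 0.72, 0.84 and 0.95.

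**Step 4: other unstated inputs.**

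- *Number analysed.* Section 3.5 requires 80% compliance, and section 3.8 adds "Outliers were removed and defined as values outside of the mean" ± 3 SD. The number analysed for lean mass is not given. If it were 27 (assumed), 3×2 power would be 0.58, 0.68, 0.81 and 0.94 at ρ = 0.5, 0.6, 0.7 and 0.8.
- *Scale of f.* If f = 0.25 describes group differences in the lean-mass change score, the 3×2 interaction is a one-way ANOVA on change with λ = 0.0625×N. Power is then 0.20 at N = 30 and 0.23 at N = 36.
- *Sphericity.* Set ρ so that the three-measurement test has power 0.80 at N = 30. The 3×2 power is then 0.70 if epsilon is 1, 0.80 at epsilon 0.75, 0.86 at 0.6 and 0.90 at 0.5.

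**The case against.** The strongest reply is that section 3.8 never says that 0.80 applies to the lean-mass group-by-time test. It says only where the effect size came from, and no primary outcome is named. Section 3.7.2 calls muscle thickness an index of hypertrophy, and that outcome does have three measurements, so lean mass may have served as a proxy. This is plausible but unstated, and it moves the gap rather than closing it: the target outcome is then unnamed and the borrowed effect size unjustified.

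The second reply is that the consequence is undetermined, and this stands. The ten-point loss holds near correlations of 0.5 to 0.6 under sphericity. It shrinks at higher correlations and can reverse if the original calculation assumed epsilon below about 0.75. If the time effect was the one powered, both designs exceed 0.80 at N = 36 and ρ = 0.5 (0.91 with three measurements, 0.83 with two). Lean mass may well be highly correlated over 12 weeks: section 3.7.1 reports a test-retest ICC of 0.994. That figure is at best an upper guide. It is not a 12-week correlation, the section does not say which device it belongs to, and the method changed from DXA to BIA after 8 scans.

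Third, the text reports a study with its participants already counted, so recalculated power cannot change the design. That is true, and it limits the remedy to correct reporting. None of these replies reconciles three measurements with a two-point outcome.

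**Conclusion.** The concern holds. The only power calculation in the plan joins an effect size from lean mass to a three-measurement design, while lean mass has two measurements and a 3×2 test. The mismatch follows from the text alone and needs no assumption.

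Its size does depend on assumptions. With f on the repeated-measures scale, sphericity, equal groups and the group-by-time test as target, power falls by about 10 points near 0.80 and by less than one point at a correlation of 0.85. Over correlations of 0.4 to 0.9, 3×2 power at N = 30 runs from 0.55 to above 0.99. The documents do not settle whether lean mass is underpowered, and nothing here shows that 36 is the wrong number. The matter should be fixed because a stated design figure is attached to the wrong test.

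**What to change.** Rewrite the sample size paragraph in section 3.8 in one of two ways.

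1. **Keep lean mass as the basis.** Redo the calculation for the group-by-time interaction with 3 groups and 2 measurements. State the pre-post correlation, the F test powered, the scale of f, and whether 36 is before or after the 15% dropout. Give power across the plausible correlation range at the number analysed for lean mass, labelled as a recalculation.
2. **Keep three measurements.** Name the 3×3 outcome that the calculation covers, use an effect size for that outcome, state the correlation and sphericity assumption, and do not present 0.80 as applying to lean mass.

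The cost is one paragraph, with no change to design, data or enrolment. The small downside is that the single figure of 0.80 becomes a range that may lie on either side of it.

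### For outcomes measured at three visits, the stated 3x3 ANOVA in effect uses only men with all three values; a likelihood-based mixed model would keep most partial records

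*Combined protocol and SAP*

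**What the plan says.** Section 3.8 has two models. The default is "A 3x2 mixed model ANOVA with group as the between subjects' factor", with pre and post as the two times. Muscle thickness, 1-RM strength, muscle power and appetite are the exceptions, "where a 3x3 mixed model ANOVA (Post-ex, Pre-sleep, Ex only x pre, mid, post) was used". Normality, equal variances and sphericity (Mauchly) are checked, and "When sphericity was violated, the main time and group x time interactions were interpreted with the Greenhouse-Geisser estimation". Values more than 3 SD from the mean are removed. The software is SPSS 25 and GraphPad Prism 8.1.1; the text does not say which program or procedure ran which model.

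On loss of data, Section 3.8 says "With an expected dropout rate of 15% (110), a sample size of 36 was adequate". Section 3.5 keeps only men with at least 80% supplement compliance in the analysis. Section 3.3 describes the participants as "N=30; Post-ex n=9, Pre-sleep n=11, Ex only n=10". The supplied text gives no method for missing values, no numbers randomised or lost, and no statement that incomplete cases were dropped or kept.

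**The concern.** Classical repeated-measures ANOVA works on complete rows. In the 3x3 models, a man who attends pre and mid but not post contributes nothing, although Section 3.1 gives the time course of adaptation as the reason for the mid assessment. Complete-row analysis is safe when loss is unrelated to response. It is not safe if men who respond poorly in the first six weeks tend to leave, and leave one arm more than another. The quantity at risk is then the group-by-time comparison, which is the question the study asks, with about 10 men per arm.

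Unequal loss is plausible by design. The compliance rule in Section 3.5 concerns supplement intake, and Ex only takes no supplement. As worded, the rule can remove men only from the other two arms.

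**Working it through.** **Inputs.** From Section 3.8: "effect size F of 0.25"; "power set to 0.8 and α set to 0.05 for 3 groups and 3 measurements"; 15% dropout; N = 36. From Section 3.3: 9, 11 and 10 men. Assumed, because not stated: the correlation between visits (rho), and the dropout mechanism.

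**1. The plan's own figure.** For repeated measures, lambda = f² × N × m / (1 − rho), with m = 3 and k = 3 groups. The group-by-time test has (k−1)(m−1) and (N−k)(m−1) degrees of freedom.
- Group-by-time, rho = 0.6, N = 30: lambda = 0.0625 × 30 × 3 / 0.4 = 14.06; df 4 and 54; power 0.83. N = 30 is the smallest equal-group size reaching 0.80.
- Time effect, rho = 0.5: N = 30 as well.
- Dropout: 30 / 0.85 = 35.3, hence 36 with equal groups.

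So 36 reproduces under either assumption; the plan does not say which effect or rho was used. It is sized to leave about 36 × 0.85 = 30.6 men. If rho is 0.5, group-by-time power is 0.82, 0.73, 0.67 and 0.61 at 36, 30, 27 and 24 complete rows. At rho 0.7 it is 0.97, 0.93, 0.90 and 0.85.

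**2. What each model can lose, and what a mixed model with baseline as covariate recovers.**

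| Model | Missing value | Lost under complete rows | Recovered |
|---|---|---|---|
| 3x2 | mid | nothing (no mid visit in model) | not applicable |
| 3x2 | post | pre | no, as no post-baseline value exists |
| 3x3 | mid only | pre and post | yes |
| 3x3 | post only | pre and mid | yes |
| 3x3 | mid and post | pre | no |
| 3x3 | pre (deleted as outlier) | mid and post | no, as the covariate is missing |

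The gain is therefore confined to the three-visit outcomes.

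**3. How often the outlier rule can act.** The largest possible |z| in a sample of n is (n−1)/√n: 2.67 for n = 9, 2.85 for n = 10, 3.02 for n = 11. Applied by arm, the 3 SD rule can remove nobody in Post-ex or Ex only, and almost nobody in Pre-sleep. Applied to all 30 men the bound is 29/√30 = 5.29, so it can act. The plan does not say which was done.

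**4. Effect on the group comparison (illustrative simulation).** Two arms of 12; three visits; unit variance; equal correlation rho; true difference in pre-to-post change 0.50 SD; 4,000 runs. Two or three of the 12 post values are missing per arm (17% or 25%). Under selective loss, men with a small pre-to-mid change are more likely to leave one arm, while the other arm loses men at random. The complete-row estimate is compared with a likelihood-type estimate that uses all pre and mid values.

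| rho | Missing | Complete rows, selective (mean) | All data, selective (mean) | SD under random loss: complete rows → all data |
|---|---|---|---|---|
| 0.5 | 17% | 0.553 | 0.498 | 0.446 → 0.438 |
| 0.5 | 25% | 0.596 | 0.511 | 0.472 → 0.457 |
| 0.7 | 17% | 0.550 | 0.504 | 0.346 → 0.340 |
| 0.7 | 25% | 0.573 | 0.503 | 0.361 → 0.353 |
| 0.9 | 17% | 0.519 | 0.494 | 0.202 → 0.199 |
| 0.9 | 25% | 0.536 | 0.496 | 0.206 → 0.203 |

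The bias is about 0.02 to 0.10 SD. Against the SD of the complete-row estimate under selective loss, it is between 0.019/0.195 = 10% and 0.096/0.469 = 20% of a standard error. Under random loss both estimates are unbiased, and the SD falls by about 1-3%. The simulated estimator does not adjust the group difference for baseline, so it illustrates the mechanism rather than the exact model proposed below.

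**The case against.** The strongest reply is that the documents never say incomplete men were dropped. No SPSS procedure is named, and Prism was also used. That stands: complete-row analysis is inferred from the sphericity test and the Greenhouse-Geisser correction. The inference is strong, since both belong to the classical procedure and nothing in Section 3.8 describes a covariance structure or a likelihood fit.

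Second, most outcomes, including lean mass (the basis of the sample size), use the pre/post model, where a mixed model recovers no men. That also stands, and limits the point to muscle thickness, 1-RM and power.

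Three stronger readings are tempting but unsupported.
- A reader might infer from 36 planned and 30 reported that six men dropped out, or from 9, 11 and 10 that the arms lost 25%, 8% and 17% of 12. The documents do not give the number randomised; the gap could be dropout, exclusion or under-recruitment. Nor do they show that any of the 30 missed a visit.
- A reader might size the bias from the worst case in which exactly the lowest 15% on mid-point gain leave: φ(z at 0.15)/0.85 = 0.233/0.85 = 0.27 SD. This is a shift in one arm's mean. It largely cancels between arms if loss is similar, and the group comparison is what matters.
- A reader might expect a large gain in precision. A pre-to-mid standard error larger by √(36/30) − 1 = 9.5% requires 36 men with pre and mid data, six of whom then left, which is not documented. For the 12-week contrast the simulated gain is 1-3%.

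**Conclusion.** The point holds for muscle thickness, 1-RM and muscular power. The stated 3x3 ANOVA in effect discards the partial records of men without a mid or post value. With selective loss from one arm, the illustrative bias in a 0.50 SD difference is 0.02 to 0.10 SD, small beside the sampling error but avoidable. With random loss almost nothing is at stake. These sizes rest on assumed correlations, 17-25% missing post values and an assumed mechanism; the actual loss is unknown.

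A mixed model deals only with loss that observed values predict. It does not correct loss driven by unobserved response, and it does not undo the 80% compliance exclusion unless the analysis set is changed too.

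**What to change.** - For the three-visit outcomes, fit a linear mixed model by REML (SPSS MIXED) with group, visit, group-by-visit and baseline value, unstructured covariance and Satterthwaite degrees of freedom. Include every randomised man with any post-baseline value. This also removes the need for the sphericity pre-test.
- Keep the 3x3 ANOVA as a sensitivity analysis.
- For pre/post outcomes the same model reduces to ANCOVA on baseline. It may improve precision, but should not be presented as recovering men.
- Make the 80%-compliance set a sensitivity analysis. This changes the analysis set, so it must be stated openly as such.
- Report the numbers randomised, lost and excluded by arm with reasons, and the number with each visit for each outcome. State whether the outlier rule is applied by arm or pooled.
- Reconcile appetite: Section 3.8 lists it under the 3x3 model, while Section 3.7.5.1 describes ratings at pre and post only.

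The cost is revised SAP wording, different syntax in the same software, and a re-run that includes men now excluded for compliance. The statistical cost is small: with two post-baseline visits the unstructured matrix has three parameters (two variances and one covariance).
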